## 1 SYNOPSIS

Title: Neuropsychological Dysfunction and Neuroimaging Abnormalities in Neurologically Intact Adult Patients With Sickle Cell Disease (SCD)

CSCC Protocol Chair: [name].

Intervention: In Phase I, approximately 156 subjects will participate in a cross-sectional study consisting of screening questionnaires, a neuropsychological testing battery, and MRI testing. In Phase II, a subset of approximately 30 participants will be asked to participate in a transfusion intervention. Half will be randomized to undergo a chronic transfusion regimen for six months, and the other half will be treated with standard care alone, guided by their disease symptoms.

Objectives:
 
Primary objective(s): To determine the extent of neurocognitive dysfunction in neurologically asymptomatic adult patients with sickle cell disease.
 
Secondary objective(s): To determine the association between neurocognitive dysfunction and imaging abnormalities.

Hypotheses/Estimates:
 
Primary hypothesis: Neurocognitive testing in neurologically asymptomatic adult sickle cell patients will be abnormal compared to community controls.
 
Secondary hypotheses:
 
 
1. Neurologically intact adults with SCD will have significantly lower scores on other neuropsychological (NP) tests of executive function than adult controls.
 
2. A larger percentage of adult patients with abnormal MRIs will have abnormal NP testing than those with normal MRIs.
 
3. Volumetric MRI will detect brain dysfunction in patients with abnormal neurocognitive tests but normal qualitative MRI.
 
4. Correction of anemia with transfusion therapy will improve the cognitive function in SCD patients with abnormal neurocognitive testing more than standard care.
 
 
Hypothesis testing will apply to the primary hypothesis only; all secondary hypotheses will address issues of estimation.


Criteria for Evaluation:
 
In the cross-sectional study, the primary endpoint is completion of baseline Wechsler Adult Intelligence Scale-Third Edition (WAIS-III) PIQ studies in 120 subjects and 36 controls. The secondary endpoints include completion of the entire baseline NP battery and MRI studies in 120 subjects and 36 controls. In the pilot intervention trial, the primary efficacy endpoint is completion of the transfusion protocol and demonstration of 5-point improvement in WAIS-III PIQ from the standard core group in 30 patients.

Study Design: This study is a cross-sectional investigation designed to compare neuropsychological function of adult neurologically normal HbSS/SB subjects with matched-peer controls. Additionally, a pilot intervention trial will randomize a subset of patients from the primary study to undergo either a chronic transfusion regimen or receive standard care alone, for six months.

Study Population: Neurologically intact adult subjects ages 21-55 years, with Hb SS/SB will be enrolled in the cross-sectional study. A subset of these subjects with WAIS-III PIQ scores less than or equal to 90 will be eligible for randomization in the pilot transfusion trial.

Sample Size: 120 subjects and 36 controls are needed to assess the primary endpoint of completion of baseline WAIS III PIQ studies. The secondary endpoints would include completion of the entire baseline NP battery and MRI studies in 120 subjects and 36 controls. Assuming a 20% attrition rate, 150 subjects and 45 controls will be recruited. After consent and randomization, the final secondary endpoint is completion of the transfusion protocol with 30 patients and demonstration of 5-point improvement in WAIS-PIQ due to transfusion above any improvement observed in a standard care group. Again, assuming a 20% attrition rate, 36 patients will be recruited.

**Title:** Neuropsychological Dysfunction and Neuroimaging Abnormalities in Neurologically Intact Adult Patients With Sickle Cell Disease (SCD)

**Data Analyses:** To test the primary hypothesis, we will use a GLM to model the data. At each site we will match the patients using a ratio of 10 patients to 3 community controls and control for site, age, sex, and education.

**Phase I Completion:** On February 22, 2008 enrollment into Phase I was completed with 120 cases and 32 controls. Enrollment and randomization into Phase II is dependent on the values obtained during Phase I, including the initial chemistry/hematology panel, MMSE, POMS, PIQ, and normal MRI. Subjects who enroll in Phase II more than 6 months (but less than 1 year) from completion of Phase I (as determined by date of WAIS-III PIQ) repeat selected assessments upon entry into Phase II. Subjects who were never enrolled in Phase I (or who completed Phase I more than 1 year ago) may also be enrolled in Phase II, per a revised set of inclusion/exclusion criteria that combine Phases I and II. The most non-invasive and least time-consuming screening assessments are completed first to ensure eligibility, before the subject moves forward with additional study procedures.

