### Observations:

1. If the standard deviation of baseline WAIS-III PIQ and six month WAIS-III PIQ is 15 in both arms and the correlation between repeated WAIS-III PIQ measurements is 0.70 in both arms, then the power to detect a five-point difference is 22%.
2. If the standard deviation of baseline WAIS-III PIQ and six-month WAIS-III PIQ is 15 in both arms but the correlation between repeated WAIS-III PIQ

measurements is 0.80 in both arms, then the power to detect a 10-point difference is 82%.

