## 13.2 STATISTICAL METHODS

The primary clinical hypothesis is that the mean score for adult patients with SCD on the WAIS-III PIQ scale will be at least one standard deviation below the mean score of a group of community controls matched for site, age, and education. We expect the adult patients with SCD will have a mean WAIS-III PIQ of 85 or less and the community control group will have a mean of 100. Although the primary hypothesis expresses the expected direction of effect, the statistical analysis will follow common practice and use a 2-sided hypothesis test with an alpha of 0.05.

To test the primary hypothesis, we will use a GLM to model the data. At each site participating in this study we will match the patients using a ratio of 3 patients to 1 community controls, but if necessary we will still statistically control for site, age, sex, and education. Model selection techniques will be used to determine the most parsimonious models. For statistical analysis we express the primary hypothesis, adult SCD patients will have an adjusted mean WAIS-III PIQ different from the community based control group adjusted mean WAIS-III PIQ (based on the final model):

$$H_0: \text{Adj\_}\mu_{\text{SCD}} - \text{Adj\_}\mu_{\text{control}} = 0$$

$$H_a: \text{Adj\_}\mu_{\text{SCD}} - \text{Adj\_}\mu_{\text{control}} \neq 0.$$

The first secondary hypothesis is the same as the primary hypothesis with other NP tests being used as the response; therefore, the analysis for these hypotheses will be the same as the primary hypothesis.

The 2nd secondary hypothesis is that patients with SCD and abnormal MRIs will have a higher proportion of abnormal NP test results than the patients with SCD and normal MRIs. The statistical analysis of this hypothesis will follow common practice and use a 2-sided hypothesis test with an alpha of 0.05. For statistical analysis we express this secondary hypothesis as:

Cortical gray matter volume, hippocampal volume, white matter lesions (WML), cortical strokes, and lacunar infarcts will correlate with cognitive function (memory and executive function).

$$H_0: \rho_{\text{MRI-NPtest}} = 0$$

$$H_a: \rho_{\text{MRI-NPtest}} \neq 0.$$

For this analysis, we will use Spearman correlations, Pearson correlations, and/or multiple regression.

The 3rd secondary hypothesis involves comparing the ability of regular MRI and VMRI to predict neurocognitive injury. The 3rd secondary hypothesis is:

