Cortical gray matter and hippocampal volume will demonstrate a more significant correlation with executive and memory cognitive functions than the correlation of WML or lacunar infarcts with these same cognitive functions.

The statistical analysis will not involve a formal hypothesis test, but in statistical terms the hypothesis can be written as:

$$H_0: \rho_{\text{MRI-Nptest-Vol}} - \rho_{\text{MRI-Nptest-Reg}} = 0$$

$$H_a: \rho_{\text{MRI-Nptest-Vol}} - \rho_{\text{MRI-Nptest-Reg}} \neq 0.$$

For this analysis, we will descriptively compare Spearman or Pearson correlations.

The last secondary hypothesis involves randomizing 36 people who had a baseline WAIS-III PIQ score  $\leq 90$  to two treatment groups. We will treat one group with transfusion for 6 months and the other group with standard care for six months. After the six months of treatment we will perform a before and after comparison of the WAIS-III PIQ results, using within subject WAIS-III PIQ change scores as the outcome. We expect that on average patients who receive transfusion will show at least a five-point improvement when retested after six months of transfusion. Although this secondary hypothesis expresses the expected direction of effect independently of the observed affect in the control group, the statistical analysis will follow common practice and first use a 2-sided hypothesis test with an alpha of 0.05 to compare the mean within subject WAIS-III PIQ change score in the two groups. Second, we will calculate a 95% CI for the true effect of transfusion on WAIS-III PIQ within subject change scores for the group who received transfusion. We will use either a t-test, a Wilcoxon Two-Sample test, or a regression model to test the hypothesis. For statistical analysis we can express this secondary hypothesis as the mean within subject change score in WAIS III PIQ for the transfusion group will be different than the mean within subject change score in the control group:

$$H_0: \mu_{\text{diff, trt}} - \mu_{\text{diff, control}} = 0.$$

$$H_a: \mu_{\text{diff, trt}} - \mu_{\text{diff, control}} \neq 0.$$

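### The synopsis confines hypothesis testing to the primary hypothesis, but 13.2 tests secondary hypotheses 1, 2 and 4 at 0.05, and the Phase II five-point endpoint is not reconciled with the test of zero difference

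*Protocol*

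**What the plan says.** **Rule on testing.** Under Hypotheses/Estimates, the protocol synopsis lists four secondary hypotheses, the transfusion hypothesis being the fourth, and then states: "Hypothesis testing will apply to the primary hypothesis only; all secondary hypotheses will address issues of estimation".

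**Section 13.2, hypothesis by hypothesis.**
- Primary: "the statistical analysis will follow common practice and use a 2-sided hypothesis test with an alpha of 0.05".
- Secondary 1 (other neuropsychological tests): the section carries the primary's analysis over to these measures, saying "therefore, the analysis for these hypotheses will be the same as the primary hypothesis". The two-sided 0.05 test therefore applies by reference.
- Secondary 2 (MRI and neuropsychological results): "The statistical analysis of this hypothesis will follow common practice and use a 2-sided hypothesis test with an alpha of 0.05".
- Secondary 3 (volumetric against regular MRI): no formal test; correlations are compared descriptively.
- Secondary 4 (transfusion): "2-sided hypothesis test with an alpha of 0.05 to compare the mean within subject WAIS-III PIQ change score in the two groups".

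Section 13.1 also writes null and alternative hypotheses for secondary 4 and computes the power of a 0.05 test. With SD 15 and correlation 0.70, "then the power to detect a five-point difference is 22" per cent. With correlation 0.80, it gives 82% power for ten points.

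**Phase II endpoint.** The synopsis (Criteria for Evaluation) gives the pilot's primary efficacy endpoint two parts. One is finishing the course of transfusions. The other reads "demonstration of 5-point improvement in WAIS-III PIQ from the standard core group in 30 patients" (taken here to mean the standard care group). Section 7.1 repeats it as an average gain at least five points above any gain under standard care. Section 13.2 uses the number differently: it expects five points in the transfused patients, says that this expectation does not depend on the control group, and adds a 95% confidence interval for the transfusion group alone.

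**The concern.** The synopsis and 13.2 cannot both be followed. A statistical analysis plan written to either one would breach the other, so this cannot simply be left to that document. As long as both stand, the study could present p-values on secondaries 1, 2 and 4 as planned tests, or disclaim them, after seeing the results.

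Phase II has a second problem of the same kind. A fixed observed gain of five points and a test of zero difference are separate yardsticks, and nothing says which one decides. The word demonstration in the endpoint suggests a finding, yet a five-point difference in 30 patients may be well inside sampling error. The reference for the five points also shifts, from the gain over standard care (synopsis, 7.1) to the change within the transfused arm (13.2).

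**Working it through.** **1. Testing rule, side by side**

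| Secondary hypothesis | Synopsis | Section 13.2 | Agree? |
|---|---|---|---|
| 1, other NP tests | estimation | two-sided 0.05, by reference to the primary | no |
| 2, MRI and NP | estimation | two-sided 0.05 | no |
| 3, volumetric MRI | estimation | descriptive, no formal test | yes |
| 4, transfusion | estimation | two-sided 0.05, also powered in 13.1 | no |

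The wording for secondary 3 shows that the authors distinguish a formal test from a descriptive comparison. The tests for the other three are therefore hard to read as loose phrasing.

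**2. Phase II inputs (all from 13.1)**

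15 completers per arm; SD 15 at both times in both arms; correlation ρ of 0.70 or 0.80; two-sided 0.05 with critical value 1.96; normal approximation.

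**3. Reproducing the stated power**

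Variance of a change score: V = 15² + 15² − 2ρ·15² = 450(1 − ρ).
Standard error of the between-arm difference: SE = √(V × 2/15).
Smallest significant difference: 1.96 × SE.

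- ρ = 0.70: V = 135; SE = √18 = 4.24; threshold 8.3 points. Power at 5 points = 1 − [Φ((8.32 − 5)/4.24) − Φ((−8.32 − 5)/4.24)] = 0.218. The protocol states 22%.
- ρ = 0.80: V = 90; SE = √12 = 3.46; threshold 6.8 points. Power at 10 points by the same formula = 0.823. The protocol states 82%.

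Both stated figures reproduce. With a t reference distribution on 28 degrees of freedom, the thresholds are 8.7 and 7.1 points.

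**4. Where the endpoint and the test part**

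| | ρ = 0.70 | ρ = 0.80 |
|---|---|---|
| Endpoint met, test not significant | 5 to 8.3 points | 5 to 6.8 points |
| No true effect: P(observed ≥ 5) = 1 − Φ(5/SE) | 11.9% | 7.4% |
| No true effect: P(significant in favour of transfusion) | 2.5% | 2.5% |
| True effect 5: P(observed ≥ 5) | 50% | 50% |
| True effect 5: P(between 5 and threshold) = Φ((threshold − 5)/SE) − 0.5 | 28% | 20% |

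**5. What estimation would deliver**

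The half-width of the 95% interval for the between-arm difference is 1.96 × SE: 8.3 points (ρ = 0.70) or 6.8 points (ρ = 0.80).

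The interval for the transfusion arm alone has SE √(V/15) = 3.0 or 2.45, so half-width 5.9 or 4.8. It is narrower, but it measures a different quantity. It includes any retest gain, and 7.1 gives separating intervention from retest effects as the reason for randomising.

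**The case against.** **Not every secondary is tested.** A reader might infer that 13.2 tests all the secondaries. It does not: secondary 3 is expressly descriptive, and for secondary 1 the 0.05 level comes only by reference to the primary. The contradiction covers three of the four.

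**The Phase II criteria are nested, not incompatible.** A reader might call them mutually exclusive. Any favourable difference above the significance threshold satisfies both, and they diverge only between 5 points and that threshold. The protocol also never states a rule for declaring transfusion effective. The five points is an expectation in 5.2.5 and 13.2 and a loosely worded endpoint in the synopsis and 7.1. The protocol calls Phase II a pilot and discloses the 22% power openly. All this stands. What remains is that the endpoint and the test are not reconciled.

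**The two five-point references could coincide.** Section 5.2.5 expects no average improvement under standard care, and then five points within the arm equals five points between arms. That holds only if the expectation is borne out, and 7.1 allows for retest effects.

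**Missing multiplicity control is not a separate fault.** A reader might go on to conclude that a chance secondary finding is very likely. The documents do not support this. They fix neither the number of scores tested nor the correlation between them, such detail is commonly left to the statistical analysis plan, and under the synopsis rule no adjustment is needed.

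**The primary analysis is untouched.** Its test, alpha and sample size do not depend on any of this. That is right, and it limits the severity.

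**Conclusion.** The point holds, and should be fixed. The synopsis reserves testing for the primary hypothesis. Section 13.2 tests secondaries 2 and 4 directly and secondary 1 by reference, and 13.1 powers secondary 4 accordingly. This part rests on the text alone and needs no assumption.

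The Phase II part depends on the protocol's own planning values: 15 per arm, SD 15, correlation 0.70 or 0.80 and the normal approximation. On these, an observed difference from 5 up to about 8.3 or 6.8 points meets the endpoint and fails the test. With no true effect, a difference of at least 5 points arises about 12% or 7% of the time, so reaching it is weak evidence of benefit. A different SD or correlation would move these figures but would not reconcile the two criteria.

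The consequence is how secondary and pilot results are labelled and read. The validity of the primary comparison is not affected.

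**What to change.** Let one rule govern the synopsis, 7.1, 13.1 and 13.2. Following the synopsis:

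- **13.2:** report secondaries 1, 2 and 4 as estimates with 95% confidence intervals, and state that no secondary result supports a confirmatory claim. As the measure of the transfusion effect, replace the interval for the transfusion group alone with the interval for the between-arm difference in PIQ change. Express the five-point expectation relative to standard care, as 7.1 does.
- **13.1:** recast the text on secondary 4 in the same way. Keep the 22% and 82% power figures only as descriptive, or replace them with the expected half-width of the between-arm interval: 8.3 points (correlation 0.70) or 6.8 points (0.80). If 13.1 is left as it is, the contradiction remains.
- **Synopsis and 7.1:** in place of demonstrating a five-point improvement, name the estimated between-arm difference in PIQ change with its 95% confidence interval.

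If the sponsor prefers to keep the tests, the synopsis sentence must change instead and the secondary p-values must be labelled nominal. The five-point endpoint would still need to be reconciled with the test.

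The cost is wording in four places and, under the first option, giving up nominal p-value claims on secondaries that the synopsis already treats as estimation. No patients, procedures or primary power are lost.

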## 2 STUDY VISIT SCHEDULE

### 2.1 Original Visit Schedule

PHASE I	Visit One	Visit Two/Visit Three	Visit Four
Consent	X		
Eligibility Screening	X		
History and Physical Exam	X		
MMSE	X		
POMS	X		
PSS	X		
Neuropsychological Battery*		X	
MRI Testing*		X	
Exit Debriefing			X

- The sequencing of the Neuropsychological Battery and the MRI is flexible, and either component can occur at Visit 2. The component that is not completed at Visit 2 will occur at Visit 3.
- Enrollment into Phase I was completed on February 22, 2008.

PHASE II	Eligibility Visit 	Transfusion Visits  or Phone Calls/Visits 	NP Battery and SF-36 Visit	MRI Testing Visit	Exit Debriefing Visit
Consent	X				
Eligibility Screening	X				
SF-36	X				
Randomization	X				
Transfusions 		X			
Phone Calls/Clinic Visits 		X			
SF-36			X		
Neuropsychological Battery 			X		
MRI Testing 			X		
Exit Debriefing					X

**1** If a subject completed Phase I > 6 months, but < 1 year ago, the subject must repeat the WAIS-III PIQ portion of the Neuropsych Battery to confirm a score of  $\leq 90$ . An additional MRI will also be done to confirm that the image does not have any new neurological events since the Phase I MRI.

**2** Number of transfusions during the six-month period will vary between six and eight, and will occur at 3- to 4-week intervals.

**3** Phone calls will occur during Months 1, 2, 4, and 5. In-person clinic visits occur during Month 3 and Month 6.

**4** The sequencing of the Neuropsychological Battery and the MRI is flexible; the NP Battery can occur before or after the MRI, as long as the two-week visit windows are maintained.

## 2.2 Revised Visit Schedule

Subjects who were never enrolled in Phase I (or who completed Phase I more than 1 year ago) may also be enrolled in Phase II per a revised set of inclusion/exclusion criteria that combine Phases I and II. The most non-invasive and least time-consuming screening assessments are completed first to ensure eligibility, before the subject moves forward with additional study procedures.

	Eligibility Visit	Visit 2 MRI	Visit 3 NP Battery/Randomization	Transfusion Visits  or Phone Calls/Visits 	Exit NP Battery Visit	Exit MRI Testing Visit	Exit Debriefing Visit
Consent Eligibility Screening PIQ MMSE POMS	X						
MRI Testing		X				X	
SF-36 Neuropsychological Battery (Randomization)			X		X		
Transfusions or Phone Calls/Clinic Visits				X			
Exit Debriefing							X

 Number of transfusions during the six-month period will vary between six and eight, and will occur at 3- to 4-week intervals.

 Phone calls will occur during Months 1, 2, 4, and 5. In-person clinic visits occur during Month 3 and Month 6.

## 4 ABBREVIATIONS

ACS	Acute Chest Syndrome
AE	Adverse Event
BTPT	Benton Tactile Performance Test
CBCL	Child Behavior Checklist
CNS	Central Nervous System
CRF	Case Report Form
CSCC	Comprehensive Sickle Cell Centers
CSF	Cerebral Spinal Fluid
CSSCD	Cooperative Study of Sickle Cell Disease
CT	Computer Topography
CVA	Cerebrovascular Accident
CVLT-II	California Verbal Learning Test - Second Edition
D-KEFS	Delis-Kaplan Executive Function Test
DSE	Double Spin Echo
DSMB	Data Safety Monitoring Board
DSST	Digit-Symbol Substitution Test
EDAS	Encephaloduroarteriosynangiosis
EEG	Electroencephalogram
FDA	Food and Drug Administration
FET	Fischer's Exact Test
FLAIR	Fluid-Attenuated Inversion Recovery
FOV	Field of View
GCP	Good Clinical Practice
GLM	Generalized Linear Model
Hct	Hematocrit
ICH	International Conference On Harmonisation
ICV	Intracranial Volume
IQ	Intelligence Quotient

IRB	Institutional Review Board
MMSE	Mini-Mental Status Examination
MRA	Magnetic Resonance Angiography
MRI	Magnetic Resonance Imaging
NHLBI	National Heart, Lung, and Blood Institute
NP	Neuropsychological
PET	Positron Emission Tomography
PI	Principal Investigator
POMS	Profile of Mood States
PRC	Protocol Review Committee
PSS	Perceived Stress Scale
RBC	Red Blood Cell
SAE	Serious Adverse Event
SAP	Statistical Analysis Plan
SB-Thalassemia	Sickle Beta-Thalassemia
SCA	Sickle Cell Anemia
SCD	Sickle Cell Disease
SD	Standard Deviation
SDMC	Statistics and Data Management Center, located at RhoFed, NC
TEA	Test of Everyday Attention
TIA	Transient Ischemic Attack
TMD	Total Mood Disturbance
TSE	Turbo Spin Echo
VMRI	Volumetric Magnetic Resonance Imaging
WAIS	Wechsler Adult Intelligence Scale
WAIS-R	Wechsler Adult Intelligence Scale - Revised
WAIS-III PIQ	Wechsler Adult Intelligence Scale - Third Edition Performance IQ
WISC-III	Wechsler Intelligence Scale for Children - Third Edition
WISC-R	Wechsler Intelligence Scale for Children Revised

---

WCST	Wisconsin Card Sorting Test
WJ-R	Woodcock Johnson Revised
WML	White Matter Lesions
WMS-III	Wechsler Memory Scales - Third Edition
WMSH	White Matter Signal Hyperintensity
WRAT-3	Wide Range Achievement Test - Third Edition

